3.9 Risk-Benefit Assessment

The risks to subjects in the present trial will be reduced by using C21 doses which have been evaluated in a recently completed Phase 1 trial (C21-003) (preliminary data) and found to have an acceptable safety profile; moreover centrally read telemetry data did not identify any clinically significant findings.

In addition, the risks will be minimised by strict compliance with the eligibility criteria and by close clinical monitoring. An independent data monitoring committee (IDMC) will also meet regularly to review the safety data and provide appropriate recommendations to the Sponsor on the overall safety of trial participants (see Section 14).

All subjects participating in the trial will be followed closely by medically qualified staff throughout the trial period (see Section 2 and Section 6.1). Adverse events will be carefully documented, and the subjects will receive relevant treatment should they occur.

IPF is a progressive, irreversible and fatal disease. Patients with IPF may receive benefit from stabilisation of their disease with C21.

Repetitive lung function measurement manoeuvres during the trial can lead to cough, shortness of breath, dizziness, or exhaustion, but since the subjects only carry out forced manoeuvres during clinic visits (not at home), these are always performed under medical supervision to ensure availability of medical aid if required. The assessments are part of the regular and well-established assessments for this patient population.

Furthermore, the protocol defines withdrawal criteria to secure the safety of subjects with severe progression of disease.

If the physician judges it necessary for the subject to receive a different treatment during the trial period, the subject will be withdrawn from the trial and receive relevant treatment.

Based on the above, it is considered ethically justifiable to include patients in the present trial, as the potential benefits of C21 are judged to balance possible disadvantages connected with participation in the trial.

Clinical Trial Protocol

Vicore Pharma AB
Trial ID: VP-C21-005

Version: 7.0
Date: 15-Sep-2021

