5.7 Withdrawal from Trial

A subject will be withdrawn from trial if any of the following occurs:

- A decline from baseline in FVC value of > 10% predicted on 2 consecutive occasions and an FVC <60% predicted (*Specific for UK*: FVC <80 % predicted ; or FVC <60% predicted for subjects previously treated with nintedanib and/or pirfenidone, or refused such treatments)
- A decline from baseline in FVC value of 5-10% predicted on 2 consecutive occasions and worsening of respiratory symptoms and FVC <60% predicted (*Specific for UK*: FVC <80 % predicted; or FVC <60% predicted for subjects previously treated with nintedanib and/or pirfenidone, or refused such treatments)
- Consistent failure to comply with dietary requirements in Section 5.4, according to the investigators
- The investigator judges it necessary due to medical reasons
- Failure to pass the medical evaluation after each 12-week treatment period (see Section 5.6.1)
- It is the wish of the subject to withdraw for any reason
- Pregnancy

An end-of-trial visit (Visit 15) must be completed for all subjects withdrawn from the trial.

Subjects withdrawn due to pregnancy will be followed – as consented to – until termination or delivery and the infant must be followed at least until the age of one month.

Subject who withdraws prior to week 12 will be replaced until 60 subjects have completed the 12-week visit.

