6.5.3 End-of-Trial (Visit 15)

Visit 15 is performed minimum 2 weeks and maximum 4 weeks after the last IMP administration.

The following procedures are performed:

- Recording of concomitant medication
- 12-lead ECG
- Blood sampling for safety and biomarker assessments (See [Table 1](#) and Section [8](#))
- Urinalysis
- Pregnancy test (beta-HCG)
- Physical examination including body weight (See [Table 1](#) and Section [8.2.4](#))
- Vital signs
- Spirometry
- Slit lamp examination
- Concomitant medication
- Reporting of AEs

If a subject is withdrawn from treatment (see Section [5.7](#)), a Visit 15 (end-of-trial visit) must be performed.

Clinical Trial Protocol

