8.2.7 Safety Laboratory Parameters

Safety laboratory parameters which are to be taken at every visit to the clinic:

- Haematology: Haemoglobin (Hb), haematocrit (erythrocyte volume fraction), platelet count (thrombocyte particle concentration [TPC]), leucocyte count, mean corpuscular volume (MCV)
- Biochemistry: Albumin, alanine transferase (ALT), aspartate aminotransferase (AST), alkaline phosphatase (ALP), bilirubin, blood urea nitrogen (BUN), calcium, creatinine, c-

Clinical Trial Protocol

Vicore Pharma AB
Trial ID: VP-C21-005

Version: 7.0
Date: 15-Sep-2021

reactive protein (CRP), gamma glutamyl transferase (GGT), glucose, lactate dehydrogenase (LD), potassium, sodium

- Urinanalysis: Dipstick for bilirubin, glucose, ketones, protein, specific gravity, urobilinogen, and pH

Any laboratory abnormality, judged by the investigator to be a clinically relevant worsening since Visit 1, should be reported as an AE if the laboratory abnormality requires clinical intervention or further investigation, unless the laboratory abnormality is associated with an already reported event.

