13.3.4 Statistical/Analytical Issues

13.3.4.1 Missing Data

To summarise the change in FVC from baseline to week 24, missing data at week 24 will be imputed assuming a decline rate of 60 mL/12 weeks for the period between last visit and week 24. No imputation will be done for the mixed model or for the safety summaries.

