13.4 Safety Analysis

13.4.1 Adverse Events

An overview of all treatment-emerging AEs including severity, relationship to IMP, serious AEs (SAEs) and AEs leading to withdrawals of treatment and withdrawal from trial or death will be presented by treatment group.

AEs will be summarised by treatment group, system organ class (according to MedDRA), and preferred term (according to MedDRA) displaying number of subjects in treatment group, number and percentage of subjects having the AE as well as number of AEs. Furthermore, AEs will be summarised according to severity, relationship, outcome, and seriousness.

SAEs and AEs leading to withdrawal from treatment will be listed and tabulated, if appropriate.

Clinical Trial Protocol

Vicore Pharma AB
Trial ID: VP-C21-005

Version: 7.0
Date: 15-Sep-2021

13.4.2 **Electrocardiogram**

12-lead ECG data will be summarised by visit including the change from baseline. The number of abnormal assessments will be summarised by visit and for changes from baseline to end-of-trial.

13.4.3 **Vital Signs**

Vital signs data (blood pressure and pulse) will be summarised by visit including the change from baseline.

13.4.4 **Laboratory Safety Assessments**

Continuous laboratory data will be summarised by visit including the change from baseline. Categorical data will be summarised by visit using frequency and percentages. Laboratory parameters will be categorised as ‘low’, ‘normal’ or ‘high’ (*i.e.* below, within, or above the reference ranges, respectively) and summarised by visit and for changes from baseline to end-of-trial in a shift table.

13.4.5 **Physical examination**

Abnormal findings on the physical examination will be summarised by visit.

14 **INDEPENDENT DATA MONITORING COMMITTEE**

An independent data monitoring committee (IDMC) has been established and will have their first meeting before the trial starts.

The functions and responsibilities of the IDMC is described in an IDMC charter.

Throughout the duration of the trial, the IDMC will evaluate all SAEs on an ongoing basis.

Further, the IDMC will monitor the overall safety of the trial during regular meetings and provide appropriate written recommendations to the Sponsor regarding trial continuation, protocol modifications or trial suspension.

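### The only laboratory shift table named in 13.4.4 ends at Visit 15, 2-4 weeks off drug, so it misses category changes that reverse after the last dose; the main table should run from baseline to the last on-treatment value

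*Combined protocol and SAP*

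**What the plan says.** Section 13.4.4 plans three laboratory summaries: continuous values and their change from baseline by visit, categorical data by visit, and low/normal/high categories "summarised by visit and for changes from baseline to end-of-trial in a shift table". No other laboratory shift table is named. Section 13.4.2 uses the same construction for ECGs: "The number of abnormal assessments will be summarised by visit and for changes from baseline to end-of-trial".

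Table 1 and Sections 5.7, 6.1 and 6.5.3 all use end-of-trial for Visit 15. Section 6.5.3 gives its timing: "Visit 15 is performed minimum 2 weeks and maximum 4 weeks after the last IMP administration". Section 5.7 extends it to early leavers: "An end-of-trial visit (Visit 15) must be completed for all subjects withdrawn from the trial".

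Section 8.2.7 introduces the tests as "Safety laboratory parameters which are to be taken at every visit to the clinic", so on-treatment samples exist at Visits 3 to 14, twelve in all. Under the same section a worsening since Visit 1 that the investigator judges clinically relevant "should be reported as an AE if the laboratory abnormality requires clinical intervention or further investigation". Section 13 leaves technical detail to a separate SAP, which is not part of the document reviewed.

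**The concern.** A shift table pairs each subject's category at baseline with a later category. If the later value is taken 2-4 weeks after stopping, the table describes what persists off drug rather than what happened on it. An effect that fades after the last dose is the kind most plausibly due to the drug: Section 9.2.2 counts improvement on dechallenge as support for a causal relationship. Such changes are the ones the table would drop.

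This matters because safety is the primary objective (4.1) and there is no control arm, so comparison with the subject's own baseline carries much of the interpretation. The Phase 1 trials in 3.5 dosed for up to 8 days, against up to 36 weeks here. At stake is a per-subject count of on-treatment changes too mild to become adverse events.

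**Working it through.** The plan gives no figure on this point, so there is none to reproduce. The check is a reading of the text followed by illustrations. The 60 subjects, the 6 affected, the reversal shares, the 2.5% rate and the correlations are assumptions.

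**1. What the table compares.** The shift table runs from baseline to end-of-trial (13.4.4). End-of-trial is Visit 15 (Table 1, 5.7, 6.1, 6.5.3). Visit 15 is 2-4 weeks after the last dose for completers and withdrawn subjects alike. Visit 14 (week 36) is the last visit of treatment period 3 (6.5.2). On this reading none of the twelve on-treatment samples enters the table.

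**2. Effect of reversal.** Take 60 subjects, 6 of them normal at baseline and high at the last on-treatment sample, with a share r back to normal by Visit 15. The Visit 15 table shows 6 × (1 − r):

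- r = 0: 6
- r = 0.5: 3
- r = 1: 0

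A table ending at the last on-treatment value shows 6 in every case.

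**3. What the by-visit rows recover.** Let b subjects be high at baseline and c high at a visit, all 60 sampled. The number newly high lies between max(0, c − b) and min(c, 60 − b).

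- b = 0, c = 6: exactly 6, nothing lost
- b = 6, c = 6: 0 to 6 (0% to 10%)
- b = 6, c = 8: 2 to 8 (3.3% to 13.3%)

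The rows therefore give the answer when nobody is abnormal at baseline and only a range otherwise. They also split a count across visits when subjects leave at different times: if 3 of the 6 in step 2 withdrew before Visit 14, the Visit 14 row shows 3 and the last on-treatment table shows 6.

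**4. Limit of a last on-treatment table.** Suppose an abnormality lasts k consecutive visits of the twelve, with its start uniform over the 13 − k possible visits. Of 6 such subjects, 6/(13 − k) are expected to be abnormal at the last visit: 0.50 for k = 1 and 0.86 for k = 6. Changes that resolve on drug are mostly missed by this table too. The by-visit rows do better here: in 200,000 simulated trials the largest row averages 1.9 of 6 for k = 1 and 5.6 of 6 for k = 6, and it is always 6 from k = 7.

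**5. Chance excursions in a worst-value table.** Assume 2.5% of values are high by chance, one baseline value and 12 on-treatment values, normally distributed with equal within-subject correlation ρ. Count subjects not high at baseline.

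- High at least once on treatment, ρ = 0: 60 × 0.975 × (1 − 0.975^12) = 60 × 0.975 × 0.262 = 15.3
- High at the last value, ρ = 0: 60 × 0.975 × 0.025 = 1.5
- For ρ > 0, average q(1 − q^12) and q(1 − q) over a standard normal u, with q = Φ((1.96 − √ρ·u)/√(1 − ρ))

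| ρ | Newly high, worst value | Newly high, last value |
|---|---|---|
| 0 | 15.3 of 60 | 1.5 of 60 |
| 0.5 | 8.5 of 60 | 1.2 of 60 |
| 0.8 | 4.2 of 60 | 0.8 of 60 |

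**The case against.** The strongest reply is that the report loses little. The same section tabulates categories by visit and change from baseline by visit. In step 2, if all six complete, the Visit 14 row shows all six. Clinically relevant worsening that needs action becomes an adverse event, investigators evaluate each out-of-range result (11.2), and the IDMC sees all available safety data (6.1). This stands, and it limits the point to the within-subject count. A reader might infer that on-treatment laboratory signals would be hidden from the report or that the primary endpoint is compromised; the planned displays support neither.

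Second, the sentence in 13.4.4 can be read as including shifts by visit, and the separate SAP may already specify on-treatment tables. That is possible, so one cannot say that no such table will exist. The wording still needs to settle it.

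Third, a reader might go further and infer that the Visit 15 table is seriously incomplete or contaminated. Safety data are not imputed ("No imputation will be done for the mixed model or for the safety summaries"), and where another treatment is needed "the subject will be withdrawn from the trial and receive relevant treatment". Both routes exist, but Visit 15 is required of everyone dosed and the documents give no rate for either. The 55 evaluable of 60 in Section 13.1 concerns FVC at week 24 and says nothing about missing laboratory samples.

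Fourth, a last on-treatment table is itself partial (step 4), and for an early withdrawal the last sample may precede the last dose by up to one visit interval. Both are true. They call for a defined window and, optionally, a supportive worst-value table.

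**Conclusion.** The point holds as a limited weakness in reporting. On its natural reading, the only named laboratory shift table counts a change that reverses off drug as no shift. By-visit summaries show most of that signal; what they cannot give is the number of distinct subjects who changed category on treatment, when some are abnormal at baseline or when affected subjects leave at different times. With 6 of 60 high both at baseline and at a visit, that number could be anything from 0 to 6.

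For ECGs the gap is smaller, because new clinically significant abnormalities are reported as adverse events (8.2.6).

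The conclusion rests on end-of-trial meaning Visit 15, which the protocol uses consistently, and on the separate SAP not already resolving it. The 60-subject denominator is illustrative: the safety set is everyone dosed (13.1), and withdrawals before week 12 are replaced until 60 complete that visit (5.7), so it can exceed 60. Priority is minor to moderate: a cheap improvement.

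**What to change.** In Section 13.4.4:

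- Make the main shift table baseline to last on-treatment value, with a pre-specified on-treatment window that includes unscheduled samples, so that completers and early withdrawals appear in one table.
- Keep baseline to Visit 15 as a separate table labelled off-treatment recovery.
- Optionally add baseline to worst on-treatment value, with worst-low and worst-high shown separately, as supportive only.

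Apply the same to abnormal ECG assessments in 13.4.2, at lower priority. If the separate SAP already contains these tables, align the protocol wording with it; if by-visit shifts are intended, say so.

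The cost is a few extra tables from data already collected, with no new visits or samples. The main drawback is that the worst-value table gathers chance excursions, which a single-arm trial has no control group to calibrate (step 5). It should therefore be read beside the last on-treatment table and not replace it.

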16 ETHICS

16.1 Independent Ethics Committees / Health Authorities

Before implementing this trial, the protocol, the proposed subject information and subject consent form, and other documents as required, will be reviewed by properly constituted independent ethics committees (IECs) and by the national regulatory authorities.

A signed and dated statement that the protocol and subject information and subject consent form have been approved by the IECs and regulatory authorities will be obtained before trial initiation.

For each individual IEC, the name and occupation of the chairman and the members of the IEC will be collected as well as a statement that the IEC works in accordance with ICH GCP.

IECs will receive updates on trial progress according to local regulations.

16.2 Informed Consent

The subject's signed and dated informed consent to participate in the trial will be obtained prior to any trial related procedure being carried out.

Before any trial related procedure the investigator will explain to the potential subject the aims, methods, reasonably expected benefits, and potential hazards of the trial and any discomfort participation in the trial may entail. Subjects will be informed that participation in the trial is voluntary and that the subject may withdraw from the trial at any time and for any reason. Subjects will be informed that if they choose not to participate, this will not affect the care the subject will receive for the treatment of his or her disease. Finally, subjects will be informed that their records may be accessed by health authorities and authorised Sponsor staff without violating the confidentiality of the subject, to the extent permitted by the applicable laws or regulations.

All subjects will be given opportunity to ask questions and will be given sufficient time to consider before consenting. The subjects may choose to be accompanied, *e.g.* by a family member, during the information process. After having consented, a copy of the informed consent form will be given to the subject.

17 AUDITS AND INSPECTIONS

A representative of the Sponsor may visit the trial site(s) at any time during the trial or after completion of the trial to conduct an audit of the trial. These audits will require access to all trial records, including source documents, for inspection and comparison with the CRFs. Subject privacy will, however, be respected. The investigator and other trial personnel will be responsible for being present and available for consultation during routinely scheduled site audit visits conducted by the Sponsor's representative.

Similar auditing procedures (inspections) may also be conducted by agents of regulatory health authorities, either as part of a national GCP compliance program or to review the results of this trial in support of a regulatory submission. The investigator should notify the Sponsor's representative or Sponsor immediately, if he/she has been contacted by a regulatory agency concerning an upcoming inspection.

Clinical Trial Protocol

18 MONITORING

Before trial initiation a monitor from the Sponsor's representative will review the protocol and the CRF with the investigators and their trial personnel. During the trial the monitor will visit the trial site regularly to check the completeness of subject records, the accuracy of entries in CRFs, the adherence to the protocol and to GCP, the progress of enrolment and the handling and accounting of IMP. Key trial personnel must be available to assist the monitor during these visits.

The investigator must give the monitor direct access to source data/documents (e.g. relevant hospital or medical records) to confirm their consistency with the entries in CRFs. No information in these records about the identity of the subjects must leave the trial site.

19 REPORTING OF RESULTS

19.1 Integrated Clinical Trial Report

Data will be reported in an integrated clinical trial report in compliance with the requirements of the current version of ICH E3: Structure and Content of Clinical Study Report ([ICH 1995](#)). The signatory investigator will review and sign the integrated clinical trial report.

The results and interpretation of the exploratory biomarker analyses may not be included in the clinical trial report but may be reported and/or published separately at a later stage.

19.2 Use of Information

All unpublished information relating to this trial and/or to the trial drug is considered confidential by the Sponsor and shall remain the sole property of the Sponsor.

The investigator must accept that the Sponsor may use the information from this clinical trial in connection with the development of the IMP, and therefore, may disclose it as required to other investigators, to government licensing authorities, to regulatory agencies of other governments, stock exchange market, and commercial partners.

19.3 Publication of Results

Basic information of this trial will be posted by the Sponsor on the website: www.clinicaltrials.gov before the first subject enters the trial.

The Sponsor is committed to publishing the trial results, whether positive or negative, in a peer-reviewed journal ([Wager, 2003](#); [Graf 2009](#)).

The criteria for authorship as set out by the Committee of Medical Journal Editors (www.icmje.org) will be applied.

The contributorship model will be applied and contributors who do not meet the criteria for authorship will be listed in an acknowledgments section with descriptions of the role of each contributor in order to ensure indexation in the National Library of Medicine.

Publications are subject to the following conditions:

Clinical Trial Protocol

Vicore Pharma AB
Trial ID: VP-C21-005

Version: 7.0
Date: 15-Sep-2021

- Data are the property of the Sponsor and cannot be published without prior authorisation from the Sponsor
- Publications should be drafted with protection of individual privacy, intellectual property, and contract rights in mind, and also conform to legislation and current national practices in patent and other laws
- The primary publication (*i.e.* the results from all centers) should be published before, or in parallel with, any secondary publications
- Publications shall not disclose any Sponsor confidential information or property

20 INSURANCE AND LIABILITY

The Sponsor has subscribed to an insurance policy covering, in its terms and provision, its legal liability for injuries caused to participating subjects and arising out of trial procedures performed in accordance this protocol, in accordance with applicable law and with the ICH Guideline E6 (Note for Guidance on Good Clinical Practice) ([ICH 1997](#)).

Clinical Trial Protocol

Vicore Pharma AB
Trial ID: VP-C21-005

Version: 7.0
Date: 15-Sep-2021

22 ABBREVIATIONS

Ab	Antibody
ADR	Adverse drug reaction
AE	Adverse event
Ag	Antigen
ALP	Alkaline phosphatase
ALT	Alanine aminotransferase
AngII	Angiotensin II
AST	Aspartate aminotransferase
AT ₁ R	Angiotension type 1 receptor
AT ₂ R	Angiotension type 2 receptor
AUC	Area under the curve
b.i.d.	bis in die (i.e. twice a day)
BMI	Body mass index
BUN	Blood urea nitrogen
CA	Competent authorities
C _{max}	Maximum plasma concentration
CRF	Case report form
CRO	Contract research organisation
CRP	C-reactive protein
CYP	Cytochrome p450
eCRF	Electronic case report form
ECG	Electrocardiography
ECM	Extracellular matrix
FAS	Full analysis set
FEV ₁	Forced expiratory volume in the first second
FVC	Forced vital capacity
GCP	Good Clinical Practice
GGT	Gamma glutamyl transferase
GMP	Good Manufacturing Practice
Hb	Haemoglobin
HBsAg	Hepatitis B surface antigen
HCG	Human chorionic gonadotropin
HCVAb	Hepatitis C virus antibody
HIV	Human immunodeficiency virus
HRCT	High-resolution computed tomography
H2RA	Histamine H2 receptor antagonist
ICH	International Conference on Harmonisation
IDMC	Independent data monitoring committee
IEC	Independent ethics committee
IMP	Investigational medicinal product
IPF	Idiopathic pulmonary fibrosis
LD	Lactate dehydrogenase
MAD	Multiple ascending dose
MCV	Mean corpuscular volume
MedDRA	Medical Dictionary for Regulatory Activities
NOAEL	No observed adverse effect level
PH	Pulmonary hypertension
PK	Pharmacokinetic
PPAS	Per protocol analysis set
PPI	Proton pump inhibitor
RP	Raynaud's phenomenon
SAD	Single ascending dose

Clinical Trial Protocol

Vicore Pharma AB
Trial ID: VP-C21-005

Version: 7.0
Date: 15-Sep-2021

SAE	Serious adverse event
SAS	Safety analysis set
SpO ₂	Oxygen saturation
SSc	Systemic sclerosis
SSc-RP	Raynaud's phenomenon secondary to SSc
SUSAR	Suspected unexpected serious adverse reaction
TEAE	Treatment-emergent adverse event
t _{max}	Maximal plasma concentration
TPC	Thrombocyte particle concentration
UIP	Usual interstitial pneumonitis
WHO	World Health Organisation

Clinical Trial Protocol

Vicore Pharma AB
Trial ID: VP-C21-005

Version: 7.0
Date: 15-Sep-2021

